4.8. Changes to Protocol Defined Analyses

No changes from the protocol defined analyses.

5. SAMPLE SIZE DETERMINATION

The target enrolment will be 1028 participants (514 in the group receiving the RSVPreF3 OA investigational vaccine co-administered with the FLU vaccine (Co-Ad group) and 514 in the Control group where RSVPreF3 OA investigational vaccine and FLU vaccine are administered staggered) to obtain at least 924 evaluable participants (462 in the Co-Ad group and 462 in Control group) for the evaluation of the primary objectives, assuming that approximately 10% of the enrolled participants will not be evaluable.

Each objective will be evaluated with a nominal type I error of 2.5%.

Table 2 Overall power to demonstrate primary objectives: non-inferiority of the immunogenicity of RSVPreF3 OA investigational vaccine when co-administered with FLU vaccine as compared to when administered alone- assuming 462 participants are available in each group

Endpoint	Standard deviation of log ₁₀ concentration	Reference ratio	Non-inferiority margin	Type II error	Power
RSV-A Non-inferiority* (1-sided test with alpha = 2.5%)					
GMTs RSV-A neutralization antibody	0.45	1.05	1.5	0.1%	99.9%
FLU Non-inferiority* (1-sided test with alpha=2.5%)					
GMTs HI H1N1 strain	0.6	1.05	1.5	2.5%	97.5%
GMTs HI H3N2 strain	0.6	1.05	1.5	2.5%	97.5%
GMTs HI B/Yamagata	0.6	1.05	1.5	2.5%	97.5%
GMTs HI B/Victoria strain	0.6	1.05	1.5	2.5%	97.5%
RSV-B Non-inferiority* (1-sided test with alpha = 2.5%)					
GMTs RSV-B neutralization antibody	0.45	1.05	1.5	0.1%	99.9%
Global Type II error to show non-inferiority					~10.0%
Global power					~90.0%

* Pass 2019 alpha = 2.5%, Two-Sample T-Tests for Non-Inferiority Assuming Equal Variance and Equal mean

For RSV: non-inferiority limit = 0.176 (=log₁₀[1.5]).

For each Flu vaccine strain: non-inferiority limit = 0.176 (=log₁₀[1.5]).

Reference Ratio= 0.0212 (=log₁₀[1.05])

Considering a slight interference of 1.05 in true GMTs in both groups with a common population standard error of 0.45 for the RSV-A and RSV-B neutralization antibodies and 0.6 for each of the FLU strains in log₁₀ transformed concentration, the study has at least 90.0% power to meet the primary objectives.

Nominal powers to evaluate secondary objective

The nominal power to evaluate the non-inferiority on seroconversion rate for each of the FLU strains is above 86%, depending on the plausible rates.

Table 3 Evaluation of non-inferiority in terms of HI antibody SCR when the FLU vaccine is co-administered with the RSVPreF3 OA investigational vaccine as compared to FLU when administered alone assuming 462 participants are available in each group for a range of plausible SCRs.

N evaluable participants per group	Threshold	Plausible rates in Control group**	Type II error	Nominal power
FLU vaccine: Non-inferiority* in terms of SCR				
462	10%	70%	8.7%	91.3%
462	10%	50%	13.9%	86.1%
462	10%	35%	11.0%	89.0%
462	10%	25%	6.1%	93.9%

SCR: Seroconversion Rate.

*Pass 2019 alpha = 2.5%, for SCR – Non-inferiority: Proportions – Two independent Proportions – Non-Inferiority Tests for the Difference Between Two Proportions based on Miettinen and Nurminen method

** SCR observed in the Control group in Zoster-004 study range from 35.3% to 60.9%.

6. SUPPORTING DOCUMENTATION

6.1. Appendix 1 Study Population Analyses

6.1.1. Participant Disposition

The number of participants who withdraw from the study will be tabulated by group according to the reason for drop-out. This analysis will be based on the ES and the PPS.

6.1.2. Demographic and Baseline Characteristics

The median, mean, range and standard deviation of age (in years) at first vaccination will be computed by group. The center distribution, distribution of participants in each age category (65-69 YOA, 70-79 YOA, ≥ 70 YOA and ≥ 80 YOA) geographical ancestry and sex composition will be presented. This analysis will be based on the ES and the PPS.

The number and percentages of participants with medical history classified by the MedDRA Primary SOC, HLT and PTs will be tabulated by group for the ES.

6.1.3. Protocol Deviations

The number of participants enrolled into the study as well as the number of participants excluded from per-protocol set (PPS) analyses will be tabulated for the total population. This analysis, also broken down by study group, will be based on the ES.

The number of participants enrolled into the study as well as the number of participants excluded from per the ES will be tabulated for the total population. This will be based on all enrolled participants.

6.1.4. Subject exposure

The number and percentage of participants who received the co-administered vaccine and the control vaccine will be tabulated by group and by vaccine for the ES.

6.1.5. Concomitant Medications

The number and percentage of participants and doses using concomitant medication (any medication, any antipyretic and any antipyretic taken prophylactically, respectively) during the 4-day follow-up period (i.e., on the day of vaccination and 3 subsequent days) and during the 30-day follow-up period (i.e., on the day of vaccination and 29 subsequent days) will be summarized by group after each vaccine dose and overall.

6.1.6. Concomitant Vaccinations

The number and percentage of participants and doses with concomitant vaccination during the 30-day follow-up period (i.e., on the day of vaccination and 29 subsequent days) will be summarized by group after each vaccine dose and overall.

6.1.7. Additional Analyses Due to the COVID-19 Pandemic

Depending on how the Covid-19 situation evolves, the SAP might be amended to reflect the analysis corresponding to Covid-19.

6.2. Appendix 2 Data Derivations Rule

This section contains standard rules for data display and derivation for clinical and epidemiological studies.

6.2.1. Attributing events to vaccine doses

The dose relative to an event is the most recent study dose given to a participant prior to the start of a given event. For example, if the start date of an adverse event is between Dose 1 and Dose 2, the relative dose will be Dose 1.

If an event starts on the same day as a study dose, the relative dose will be derived from the additional information provided in the case report form (CRF) using the contents of the flag indicating if the event occurred before or after study dose. If 'after study dose' is selected, the relative dose for the event will be the one administered on the start day of the event. If 'before study dose' is selected, the relative dose for the event will be the dose prior to this one.

6.2.2. Handling of missing data

6.2.2.1. Dates

When partially completed dates (i.e. dates missing a day and/or month) are used in calculations, the following standard rules will be applied:

- A missing day will be replaced by 15
- A missing day and month will be replaced by June 30th.

The following exceptions apply:

When partially completed dates (i.e. with missing day or month) are used in calculations, the following rules will be applied:

- Adverse event start dates with missing day:
 - If the month is not the same as the vaccine dose, then the imputed start date will be the 1st of the month.
 - If the event starts in the same month as the vaccine dose, the flag indicating if the event occurred before or after vaccination (AE.AESTRTPT) will be used to complete the date. If 'after vaccination' is selected, the imputed start date will match the vaccine dose given during that month. If 'before vaccination' is selected, the imputed date will be one day before the vaccine dose given during that month.
- Adverse event start dates with missing day and month:
 - If the year is not the same as the vaccine dose, then the imputed start date will be the 1st of January.
 - If the event starts in the same year as the vaccine dose, the flag indicating if the event occurred before or after vaccination (AE.AESTRTPT) will be used to complete the date. If 'after vaccination' is selected, the imputed start date will match the first vaccine dose given during that year. If 'before vaccination' is selected, the imputed date will be one day before the first vaccine dose given during that year.
- Adverse event end dates with missing day: the imputed end date will be the last day of the month (30 or 31) or the study conclusion date whichever comes first.
- Adverse event end dates with missing day and month: the imputed end date will be the last day of the year (31st of December) or the study conclusion date whichever comes first.

All incomplete concomitant medication/vaccination start/end date will follow the rules above.

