3. ANALYSIS SETS

Analysis Set	Definition / Criteria
Enrolled set*	Participants who agreed to participate in a clinical study after completion of the informed consent process.
Safety/Exposed set (ES)	All participants who received a study intervention. Analysis per group is based on the study intervention administered.
Per-Protocol set (PPS)	All eligible participants who received at least one study intervention as per-protocol in the control group and all study interventions in the Co-Ad group , had immunogenicity results pre-post-dose for at least one antigen, complied with blood draw intervals (refer to intervals mentioned below) and contribution of participants to PPS at specific timepoint will be defined by timepoint, without intercurrent medical conditions that may interfere with immunogenicity and without prohibited concomitant medication/vaccination.

*All participants enrolled and included in the database will be part of the enrolled set.

Intervals for the Co-Ad group: Visit1-Visit2=30-37 days

Intervals for the Control group: Visit1-Visit2=30-37 days, Visit2-Visit3=30-37 days

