- The number of days with solicited events ongoing beyond the 4-day follow-up period will be tabulated for each individual solicited event using descriptive statistics (mean, minimum, Q1, median, Q3, maximum). The same computations will be done for Grade 3 solicited events.

- The number and percentage of participants with any unsolicited AEs during the 30-day follow-up period (i.e. the day of vaccination and 29 subsequent days) with its exact 95% CI will be tabulated by group and by Medical Dictionary for Regulatory Activities (MedDRA) System Organ Class (SOC), High Level Term (HLT) and Preferred Term (PT). Similar tabulation will be done for Grade 3 unsolicited AEs, for any causally related unsolicited AEs, for Grade 3 causally related unsolicited AEs and for unsolicited AEs resulting in a medically attended visit. The verbatim reports of unsolicited AEs will be reviewed by a physician and the signs and symptoms will be coded according to the MedDRA Dictionary for Adverse Reaction Terminology. Every verbatim term will be matched with the appropriate Preferred Term. The above analysis by dose will also be performed.
- The number and percentage of participants with at least one report of SAE classified by the MedDRA Primary SOC, HLT and PTs and reported after vaccine administration (Day 1) up to study end (6 months after last vaccination) will be tabulated with exact 95% CI.
- The number and percentage of participants with at least one report of causally related SAE classified by the MedDRA Primary SOC, HLT and PTs and reported after vaccine administration (Day 1) up to study end (6 months after last vaccination) will be tabulated with exact 95% CI.
- The same tabulation will be presented for fatal SAEs.
- All SAEs will also be described in detail in a tabular listing.
- All pIMD will also be described in detail in a tabular listing.
- All AEs/SAEs leading to study/intervention discontinuation from dose 1 up to study end will be tabulated.
- The percentage of participants with at least one report of pIMD classified by the MedDRA SOC, HLT and Preferred Terms and reported after vaccine administration (Day 1) up to study end (6 months after last vaccination) will be tabulated with exact 95% CI.
- The percentage of participants with at least one report of related pIMD classified by the MedDRA SOC, HLT and Preferred Terms and reported after vaccine administration (Day 1) up to study end (6 months after last vaccination) will be tabulated with exact 95% CI.

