6.2.3.6. Onset day

The onset day for an event (e.g. AE, concomitant medication/vaccination) is the number of days between the last study dose and the start date of the event. This is 1 for an event occurring on the same day as a study dose (and reported as starting after study dose).

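### The partial-date rule in SAP 6.2.2.1 is written for one dose; in Control it can date an after-FLU adverse event outside the 30-day window when the RSV dose is given 31 or more days after FLU (minor)

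*SAP*

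**What the plan says.** SAP 6.2.2.1 (Dates) gives these rules for incomplete adverse event start dates:

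- Day missing, no dose in that month: "If the month is not the same as the vaccine dose, then the imputed start date will be the 1st of the month".
- Day missing, dose in that month, flagged as before: "If 'before vaccination' is selected, the imputed date will be one day before the vaccine dose given during that month". If flagged as after, the date becomes the dose date.
- Day and month missing, same year as a dose, flagged as after: "the imputed start date will match the first vaccine dose given during that year".

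The rules speak of the vaccine dose in the singular. They set no floor at a previous dose and do not say which dose the before/after flag refers to.

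Other relevant provisions:

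- SAP 6.2.1: "The dose relative to an event is the most recent study dose given to a participant prior to the start of a given event". For events starting on a dose day, a flag of before sends the event to the preceding dose.
- SAP 6.2.3.6, on onset day: "This is 1 for an event occurring on the same day as a study dose".
- SAP 4.3.2: unsolicited events are tabulated "during the 30-day follow-up period (i.e. the day of vaccination and 29 subsequent days"), by group and by dose, on the Exposed Set.
- SAP 3: "Intervals for the Control group: Visit1-Visit2=30-37 days". Protocol Table 4 plans 30 days, and Protocol Section 8 allows 30 more days for the Control RSV dose in special circumstances.
- Co-Ad participants receive both vaccines on Day 1 and have no second dose date.

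**The concern.** With a single dose, an event flagged as before vaccination precedes all study vaccine, and dating it to the eve of the dose does no harm. With two doses, an event can be before the second dose and still follow the first. The rule then places it at the latest date compatible with the flag, which can be beyond the first dose's 30-day window. Such an event also precedes RSV, so it is counted after neither dose and drops out of the Control 30-day total.

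Co-Ad events in the month after vaccination take the 1st of that month, the earliest compatible date. Identical missing data are therefore handled in opposite ways in the two groups, in tables that serve the secondary objective of comparing the safety of co-administered and separate vaccination.

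The missing-month rule raises a different question. When both Control doses fall in one calendar year, an event that followed RSV can be credited to FLU.

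**Working it through.** **Day numbering.** The dose day is Day 1, so an RSV dose k days after FLU falls on FLU Day k + 1. At k = 30 this gives Day 31, which matches the plan's stated RSV day. The day before RSV is FLU Day k.

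**Window check.** The event remains attributed to FLU, so onset Day k is compared with Days 1-30:

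- k = 30: Day 30, inside.
- k = 31 to 37: Days 31 to 37, outside.
- Extended intervals: outside, wherever a truly in-window event can still share a calendar month with the RSV dose.

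**Example.** First dose on 20 October, true onset on 5 November (Day 17), day missing:

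| Case | Imputed date | Onset day | Counted? |
|---|---|---|---|
| Co-Ad | 1 November | 13 | yes |
| Control, RSV 19 November (k = 30) | 18 November | 30 | yes |
| Control, RSV 22 November (k = 33) | 21 November | 33 | no |

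**Share lost.** Let m be the day of the month of the RSV dose. True onsets in that month and before RSV are FLU Days k - m + 2 to k. Those also within Day 30 number m - 1 - (k - 30), or zero if negative. For k of 31 or more, all of them are lost. In the example with k = 33 and m = 22, this is 21 - 3 = 18 of the 30 possible onset days (Days 13 to 30).

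Taking a 30-day month with m evenly spread over 1 to 30 and onset evenly spread over Days 1-30, there are 900 combinations:

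- k = 31: 1 + 2 + ... + 28 = 406, and 406/900 = 45.1%.
- k = 33: 1 + 2 + ... + 26 = 351, and 351/900 = 39.0%.
- k = 37: 1 + 2 + ... + 22 = 253, and 253/900 = 28.1%.

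Enumerating real calendar dates agrees. The percentages are shares of all in-window missing-day Control events:

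| First-dose dates | k = 30 | k = 31 | k = 33 | k = 37 | Mean, k = 30-37 |
|---|---|---|---|---|---|
| 181 days from 1 October | 0% | 45.5% | 39.3% | 28.4% | 32.1% |
| Full year | 0% | 45.8% | 39.7% | 28.8% | 32.4% |

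Co-Ad loses 0% in every case, because its imputed date is never later than the true onset.

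**Dependence on actual intervals.** Now restrict to in-window missing-day Control events in the RSV month. Suppose a proportion p of RSV doses is given at exactly 30 days and the rest are spread evenly over 31-37 (full-year enumeration). The loss is 0% at p = 1, 33% at p = 0.6, 53% at p = 0.4, 84% at p = 1/8 and 100% at p = 0. It exceeds one half only if p is below about 0.43.

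**Absolute size.** The missing-day rate is not in the documents. Assuming 1% to 5% and the 32% average, 0.01 x 0.32 = 0.3% to 0.05 x 0.32 = 1.6% of Control after-FLU events would drop out. At the planned interval the figure is zero.

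**Day and month both missing.** With FLU on 20 October and RSV on 22 November of one year, an event after RSV in that year, flagged as after, is dated 20 October, which is FLU Day 1. It still counts in the Control total but moves from RSV to FLU. If the doses straddle the year end and the event is in the second year, the first dose of that year is RSV and nothing is misattributed.

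**The case against.** Several counter-arguments are sound:

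- **The planned schedule loses nothing.** A reader might infer that most of these events are pushed out, since seven of the eight allowed intervals fail. The documents give no distribution of actual intervals, and the loss among RSV-month events can be anything from 0% to 100%.
- **There is no fixed direction.** A reader might infer a one-way bias in the by-dose tables. The missing-day rule removes events from the Control after-FLU table, but the missing-month rule adds events to it. Nor does the first mechanism favour co-administration: fewer counted Control events make Co-Ad look relatively worse.
- **The meaning of the flag is assumed.** Reading it relative to the RSV dose follows SAP 6.2.1, but that section covers same-day events only, and the case report form is not among the documents. If a site selected after because the event followed FLU, the event would be dated to the RSV dose. That is misattribution and not loss, and it is still an error.
- **Few events qualify.** The day must be missing, the month known and equal to the RSV month, the flag before, and k at least 31. Control diaries are checked and participants interviewed at Visit 2, the RSV-dose visit, which should limit missing days.
- **The tables are descriptive.** They count participants, so someone with another in-window event remains in the overall row, and no between-group safety test is specified. If 20% of 514 Control participants (about 103) had one after-FLU event each, 0.3% to 1.6% is about 0.3 to 1.6 participants.

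These points limit the size of the problem. They do not remove it: the rule as written misdates a defined class of events in one group only.

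**Conclusion.** The point holds as a minor defect. Under SAP 6.2.2.1, a missing-day Control event in the RSV month, flagged as before RSV, is dated to FLU Day k. It is kept at k = 30 and lost at k = 31 to 37 and at extended intervals, while Co-Ad never loses the corresponding event. Among in-window missing-day Control events the loss is 0% at the planned interval and about 28% to 45% at 31 to 37 days. This rests on evenly spread first-dose dates and onset days and on the flag referring to the RSV dose.

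The documents do not support saying that most such events are lost, or that the net effect on the after-FLU table has a known sign. The absolute effect cannot be derived from them and is probably small. Among the adverse event outputs, the loss reaches only the 30-day unsolicited event tables. SAE and pIMD tables running to study end do not use that cut-off. The missing-month rule is a separate matter of dose attribution.

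**What to change.** Amend SAP 6.2.2.1 as follows:

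1. State which dose the before/after flag refers to when a participant has two dose dates.
2. For a Control event with the day missing, flagged as before RSV and after FLU, impute the later of the 1st of that month and the FLU dose date. This is never later than the true onset, so no truly in-window event is lost at any interval, and it matches what Co-Ad already receives.
3. When day and month are both missing, impute the RSV dose date only if the dose flag shows that the event followed RSV. First report at Visit 3 or at the Month 7 contact is not enough, because an event can begin before RSV and be reported later.

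The cost is a few sentences in the SAP and a small programming change, with no new data collection provided that the existing flag can be tied to a specific dose. It should be settled before database lock.

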6.2.2.2. Laboratory data

Missing laboratory results (including immunological data) will not be replaced.

6.2.2.3. Daily recording of solicited events

6.2.2.3.1. *Studies with paper diaries*

For studies using paper diaries which have questions in the CRF indicating the presence or absence of solicited events, the following rules are applicable for all solicited events except fever:

- Denominators for the summary of administration site (or systemic) solicited events will be calculated using the number of participants who respond “Yes” or “No” to the question concerning the occurrence of administration site (or systemic) events.
- When a specific solicited event is marked as having not occurred following a specific study dose (i.e. SDTM CE.CEOCCUR=N for the specified post-dose period for the event in question), all daily measurements will be imputed as None.
- When a specific solicited event is marked as having occurred following a specific study dose (i.e. SDTM CE.CEOCCUR=Y for the specified post-dose period for the event in question), any missing daily recordings will be given imputed values to allow them to contribute to the ‘Any’ rows but not to specific grade rows of the solicited event summary tables.
- When the group of solicited events (administration site or systemic) occurred is missing (i.e. SDTM CE.CEOCCUR=""), all missing daily recordings will be considered as missing for the solicited event summary tables.

The following table shows how participants contribute to each category for a specific solicited event over the Day X to Day Y post-dose period:

Solicited event category	Participants included in the calculation of the numerator
Any	All participants with at least one occurrence of the adverse event at Grade 1, Grade 2, or Grade 3 between Day X and Day Y or with the adverse event marked as present and at least one missing daily recording between Day X and Day Y
At least Grade 1	All participants with at least one occurrence of the adverse event at Grade 1, Grade 2, or Grade 3 between Day X and Day Y
At least Grade 2	All participants with at least one occurrence of the adverse event at Grade 2 or Grade 3 between Day X and Day Y
At least Grade 3	All participants with at least one occurrence of the adverse event at Grade 3 between Day X and Day Y

For fever, the summary tables will not include the row ‘Any’. The missing daily records do not contribute to the number participants reporting fever by half degree (°C): >=38; >38.5, >39, >39.5 and >40.

